5.6 Statistical models

5.6.1 Primary analysis

The primary statistical hypothesis for ASAS 20 being tested is that there is no difference in the proportion of patients fulfilling the ASAS 20 criteria at Week 12 in the Secukinumab 300 mg treatment group versus placebo group.

The primary analyses will be conducted via logistic regression with treatment and concomitant MTX intake status as factors. The Odds ratio, 95% confidence interval (CI) and p-value will be presented comparing secukinumab 300 mg treatment group to placebo group at Week 12.

SAS Code for logistic model

```
Proc logistic data=aaa;
Class TRT STRATA / param=glm;
Model AVAL = TRT STRATA;
Lsmeans TRT / diff cl exp;
Ods output diffs=lsm_diff;
Run;
```

In cases where separation is a concern for the primary endpoint at Week 12, e.g. 0% or 100% response in one treatment (sub)group, an exact logistic regression model will be applied to all visits. To ensure convergence, this model will not include any continuous covariates.

```
Proc logistic data=aaa exactonly;
```

```
Class TRT STRATA / param=glm;  
Model AVAL = TRT STRATA;  
Exact TRT / estimate=both;  
Ods output exactoddsratio=exactoddsratio;  
Run;
```

Missing data for ASAS 20 response for data up to Week 12 will be handled by multiple imputations technique.

Multiple Imputation

A multiple imputation will be performed based on MAR by treatment group for baseline weight, baseline and post-baseline of each parameter for visits up to the primary time point of 12 weeks using Markov Chain Monte Carlo (MCMC) method with EM algorithm.

Impute the missing values 100 times (NIMPUTE) with a seed=457<studycode> as shown below:

```
proc mi data= min=<min of scale> max=<max of scale> out=imp minmaxiter=100000  
nimpute=100 seed=4572310;  
by trt;  
var weight_base var1_base var1_week1-var1_week16;  
mcmc chain=multiple initial=em;  
run;
```

If needed repeat for each component necessary to calculate the final score, e.g. as follows:

```
proc mi data=imp min=<min of scale> max=<max of scale> out=imp2 minmaxiter=100000  
nimpute=1 seed=4572310;  
by trt_imputation_;  
var weight_base var2_base var2_week1-var2_week16;  
mcmc chain=multiple initial=em;  
run;
```

The score and ASAS response can now be calculated based on the complete data. The response rate will be calculated for each imputation and then combined using Rubin's rules. In order to calculate the response rate for each imputation, PROC FREQ will be used as follows.

Calculate binomial proportion and standard error for each imputation.

```
proc freq data=<ASAS20>;  
by treat visit_imputation_;  
tables <response> / binomial (level=2 cl=wilson correct) ;  
ods output BinomialProp=imp_bpr;  
run;
```

Transpose the dataset for subsequent use with PROC MIANALYZE.

```
proc transpose data=imp_bpr out=imp_trs(drop=_name_) ;
by treat visit _imputation_ ;
var nvalue1; id name1; idlabel label1;
run;
```

Apply LOGIT transformation: $y = \log(p/(1-p))$ and std. err. transformation: $\text{se} = \text{se}/(p^*(1-p))$

```
data logit;
set imp_trs(rename=(_bin_=p e_bin=se));
by treat visit _imputation_ ;
lmean=log(p/(1-p));
lse=se/(p*(1-p));
run;
```

The transformed binomial proportion estimates and standard errors are combined by applying Rubin's rules for multiple imputed data sets.

```
proc mianalyze data=logit;
by treat visit ;
modeleffects lmean;
stderr lse;
ods output ParameterEstimates=logitres;
run;
```

The combined data should be transformed back using the following formula: $p = 1/(1+\exp(-y))$

```
data miexpress;
set logitres;
by treat visit ;
resti = 1/(1+exp(-estimate));
rlow = 1/(1+exp(-lclmean));
rupp = 1/(1+exp(-uclmean));
run;
```

Of note, sometimes all responses may be imputed to 0 or 1 at a given combination of response variable, treatment group and visit. Such cases should be considered separately. The combined final response rate would be the same as the original response but the 95% CI will be undefined.

The odds ratio will be derived using GENMOD for each imputation, then combined using Rubin's rules again.

```
proc genmod data = asas20_mi descending;
by avisitn_imputation_;
class trt_TNFRESN ;
model aval = trt_TNFRESN weight / link=logit dist=bin;
lsmeans trt_ / diff;
estimate 'AIN457 75mg mg vs Placebo' trt_ 1 0 -1;
estimate 'AIN457 150mg mg vs Placebo' trt_ 0 1 -1;
ods output Estimates=imp_est;
run;
```

```
proc mianalyze data=imp_est;
by avisitn trt_ ;
modeleffects LBetaEstimate;
stderr StdErr;
ods output ParameterEstimates=res;
run;
```

For sensitivity analysis, the above code will be used for non-responder imputation. In addition to that, the above analysis will also be performed for each baseline variables (e.g: sex, age class, disease severity at Baseline).

Non-parametric ANCOVA model

A non-parametric ANCOVA model ([Koch 1998](#)) will be used as sensitivity analysis for ASAS 20 and possibly also for continuous endpoints that are not normally distributed. The macro NParCov3 will be used ([Zink 2012](#)).

For continuous response variable, the macro call will be as follows:

```
%NParCov3(OUTCOMES = response, COVARS = weight baseline, C = 1, HYPOTH = ALT,
STRATA = TNF $\alpha$  status, TRTGRPS = treatment, TRANSFORM = NONE, COMBINE = FIRST,
DSNIN = RESP, DSNOUT = OUTDAT);
Data set _OUTDAT_DEPTEST provides results for the treatment difference, and
_OUTDAT_CI provides a 95% confidence interval for the treatment estimate.
```

For binary response variable, the macro call will be as follows:

```
%NParCov3(OUTCOMES = response, COVARS = weight, C = 1, HYPOTH = ALT,
STRATA = TNF $\alpha$  status, TRTGRPS = treatment, TRANSFORM = LOGISTIC, COMBINE = FIRST,
DSNIN = RESP, DSNOUT = OUTDAT);
```

The odds ratio and confidence interval are to be obtained from _OUTDAT_RATIOCI.

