2.5.3 Handling of missing values/censoring/discontinuations

Missing data for ASAS 20 response for data up to Week 12 will be handled by multiple imputations technique.

Multiple imputation is a simulation based approach where missing values are replaced by multiple Bayesian draws from the conditional distribution of missing data given the observed data and covariates, creating multiple completed data sets. These completed data sets can then be analyzed using standard methods. Within this analysis, the ASAS composites will be imputed and response variables will be derived based on the imputed scores. In the multiple imputation analysis, the response status will be imputed based on the individual treatment arm information.

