5.5 Score derivations and response criteria

5.5.1 Assessment of Spondyloarthritis International Society (ASAS)

The ASAS response measures consist of the following assessment domains ([Sieper et al 2009](#)):

[figure not shown]
1. Patient's global assessment of disease activity measured on a VAS scale.
2. Patient's assessment of IBP, represented by either total or nocturnal pain scores, both measured on a VAS scale.
3. Function represented by BASFI average of 10 questions regarding ability to perform specific tasks as measured by VAS scale.
4. Morning stiffness, represented by the average of the last 2 questions on the 6-question BASDAI regarding morning stiffness as measured by VAS scale.

[figure not shown]
ASAS response criteria (ASAS 20)

The ASAS Response Criteria (ASAS 20) was defined as an improvement of $\geq 20\%$ and ≥ 1 unit on a scale of 10 in at least 3 of the 4 main domains and no worsening of $\geq 20\%$ and ≥ 1 unit on a scale of 10 in the remaining domain.

ASAS response criteria (ASAS 40)

The ASAS 40 response was defined as an improvement of $\geq 40\%$ and ≥ 2 units on a scale of 10 in at least 3 of the 4 main domains and no worsening at all in the remaining domain.

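### The primary multiple imputation models each ASAS domain on its own and loses the between-domain correlation that the 3-of-4 ASAS 20 rule depends on; the effect is small

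*SAP*

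**What the plan says.** SAP section 2.5.3 imputes at component level: "the ASAS composites will be imputed and response variables will be derived based on the imputed scores". Section 2.6.3 applies the same method to the key secondary 150 mg comparison, and section 2.7.3 uses multiple imputation for ASAS 40. Section 5.5.1 defines ASAS 20 as improvement "in at least 3 of the 4 main domains and no worsening of" a set size in the remaining domain.

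Section 5.6.1 gives the code. The first PROC MI call, run by treatment, has "var weight_base var1_base var1_week1-var1_week16" with "nimpute=100 seed=4572310". The SAP then says "If needed repeat for each component necessary to calculate the final score" and prints a second call, run by treatment and imputation number, with "var weight_base var2_base var2_week1-var2_week16" and "nimpute=1 seed=4572310". That call reads the data set that already holds the imputed first component but leaves the component out of its variable list.

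The prose above the code agrees with this one-component-at-a-time structure. It limits the imputation to "baseline and post-baseline of each parameter for visits up to the primary time point of 12 weeks", whereas both variable lists run to Week 16.

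**The concern.** ASAS 20 is a property of the joint distribution of four domains. In real patients the domains move together, so many patients improve in most of them or in few. If missing domains are drawn independently, more imputed patients end with a mixed pattern, such as two of four improved, which fails the rule. The imputed response rate then falls, and it falls further on placebo, where each domain is less likely to improve. At the planned rates this inflates the apparent benefit.

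When only one component is missing at Week 12 (a case named as deviation OTH02a in section 5.7), the patient's three observed Week 12 domains do not inform the imputation.

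This is the missing-data method for both confirmatory tests. Its result also depends on how a repeated seed behaves across calls, which a pre-specified primary analysis should not leave open.

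The Week 16 end of the variable lists is a separate mismatch between text and code. By Week 16 placebo patients have been re-randomised to active drug (section 1.1). No bias is claimed from it.

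**Working it through.** **Inputs from the SAP.** ASAS 20 rates of 40% (placebo), 60% (300 mg) and 57% (150 mg); 150 per group needed and 165 recruited; two-sided 5% (section 3). Visits are baseline and Weeks 1, 2, 3, 4, 8 and 12 (Table 2-1).

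**Assumed, because the SAP gives no value.** Missing share m = 15/165 = 9.1% in both arms; domain correlation 0.5, 0.65 or 0.8; correlation of a domain's Week 12 score with its own earlier score of 0.32–0.52 (baseline), 0.53–0.81 (Week 4) and 0.69–0.87 (Week 8); baseline mean 6.5 (SD 1.6); Week 12 SD 2.3.

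**1. The plan's own figures.** Exact enumeration of Fisher's test at 150 per group gives 92.9% power for 60% vs 40% (stated 92%) and 82.6% for 57% vs 40% (stated at least 80%). Both agree with the SAP.

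**2. Formula.** With q the response rate among imputed patients, bias in the difference = m × [(q300 − 60%) − (q0 − 40%)].

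**3. Independent draws, full ASAS 20 rule, 100,000 simulated patients per setting.** Central setting (domain correlation 0.65, middle own-domain correlations, scores clipped to 0–10):

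| Last observed visit | Placebo (true 40%) | 300 mg (true 60%) | Bias in points |
|---|---|---|---|
| Week 8 | 34.5% | 56.8% | (−3.2 + 5.5) × 0.0909 = +0.21 |
| Week 4 | 31.8% | 55.3% | (−4.7 + 8.2) × 0.0909 = +0.32 |
| Baseline only | 25.5% | 52.5% | (−7.5 + 14.5) × 0.0909 = +0.64 |

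Over all settings the bias is +0.13 to +0.33 (history to Week 8), +0.23 to +0.48 (to Week 4) and +0.53 to +0.82 (baseline only). Joint draws return 39.7–40.5% and 59.7–60.4%.

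**4. Scale.** SE = √(2 × 0.6 × 0.4/165) = 5.4 points, so the bias is 0.13/5.4 = 0.02 to 0.82/5.4 = 0.15 SE. Coverage of the 95% interval stays at or above 94.7%.

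**5. Odds ratio, equal mix of the three histories.** Mean imputed rates are 30.6% and 54.9%. Whole-arm rates are (150 × 0.40 + 15 × 0.306)/165 = 39.1% and (150 × 0.60 + 15 × 0.549)/165 = 59.5%. The odds ratio moves from 2.25 to 2.29.

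**6. Finite-sample check.** With 165 per arm, 15 missing (5 per history), Bayesian normal-regression imputation by arm, 20 imputations and 1,500 replicates, separate calls give +0.42 points (Monte Carlo SE 0.04). A joint model thinned to baseline, Week 4 and Week 8 gives −0.05 (0.04).

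**7. Different models.** A latent-threshold model (domain correlation 0.3–0.8, own-history R² 0–0.7) gives +0.11 to +0.82, and a 0–10 scale model gives +0.08 to +0.74. In the 0–10 scale model, chi-square power at 165 per group moves from 95.6% to between 95.8% and 96.8%.

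**8. Shared random stream.** If the calls for domains 2–4 share a stream, the difference among imputed patients moves by −3.0 to +1.6 points. Multiplied by 0.0909, that is −0.27 to +0.15 overall. If all four domains use identical draws, the two models in step 7 give −0.02 to −0.53 overall.

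**9. Other cases, independent draws.**
- 57% vs 40%: +0.09 to +0.65.
- 5% missing: +0.07 to +0.45. 15% missing: +0.2 to +1.35.
- 20% missing on active and 5% on placebo (illustrative): −0.1 to −1.2.
- One component missing: 5–14% of such patients get the wrong response status, against 3–11% if the other domains are used.
- ASAS 40, difference among imputed patients: −0.4 to −6.0, or −0.04 to −0.55 overall after × 0.0909.

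**The case against.** The strongest reply is that this does not matter in practice. On the figures above the error is at most 0.15 SE, the central odds ratio moves only from 2.25 to 2.29, and nothing is lost when the arms have equal rates and equal missingness, so type I error is not raised by this alone. That stands and limits the weight of the point.

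The direction is also not fixed. If the second call is repeated as printed for domains 2–4, those calls share a seed, and a shared stream is a fair reading. This stands too, so the overstatement is conditional on independent draws.

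The upper end needs every missing patient to have baseline data only. The 9.1% treats the whole reserve as missing data, although section 3 sets it aside for protocol violations as well and section 2.4.2 lets rescued patients stay in assessment to Week 12. True missingness may well be lower, and the bias scales with it.

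The code can be read as a template with placeholders. That carries less weight: the prose describes the same component-wise imputation, and no section supplies a joint model.

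A full joint model is large: 4 domains × 7 visits + weight = 29 variables and 29 × 30/2 = 435 covariance terms. The check in step 6 used a thinned visit set and normal regression, not MCMC with score limits. If the limits are applied by redrawing while true scores pile up at 0, separate calls give +1.4 to +6.8 points among imputed patients and joint draws give −0.2 to −3.2. Joint imputation alone does not remove that part.

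The non-responder sensitivity analysis needs no imputed scores and is a partial safeguard, but it does not correct the primary estimate.

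**Conclusion.** The concern holds. As written, the primary imputation omits a correlation that the ASAS 20 rule depends on. With independent draws and 9.1% missing in both arms, the 60% vs 40% difference is overstated by about 0.1 to 0.8 points. With a shared stream the error is smaller or reversed, and the SAP does not say which applies. Every magnitude rests on assumed correlations, drop-out times and missingness. The effect would not change the conclusion at the planned effect size. The method should still be corrected, because it serves both confirmatory tests and its result turns on an unstated property of the random-number generator. The Week 12 versus Week 16 mismatch is a separate correction of text and code.

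**What to change.** Impute the four ASAS domains jointly by randomised arm: one PROC MI call, one variable list holding all domains and baseline weight, one seed. Use the same imputed data for ASAS 20 (both doses) and ASAS 40.

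If the full list may not converge, name the reduced visit set in advance. Baseline and Weeks 4, 8 and 12 give 4 × 4 + 1 = 17 variables, and thinning to those earlier visits was stable and unbiased at 165 per arm in the check above. State also how the score limits are applied, since joint imputation does not settle that.

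As a separate correction, end the variable list at Week 12, as the text already says.

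The cost is a SAP code revision and a convergence test, to be done before the Week 12 database freeze and unblinding (section 2.1). No new data are needed and sample size is unaffected.

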An overall type I error (2-sided) 5% will be used to control type I error. Since two secukinumab doses will be tested versus placebo in a hierarchical manner, no type-I-error adjustment is required for each comparison with respect to the primary endpoint (ASAS 20 response at Week 12). To achieve 92% power and assuming conservatively a response rate of 40% in the placebo group, at least 150 patients per group would be needed under equal allocation to show a response rate of 60% in the secukinumab 300 mg group. Using the same number of patients per group, the second test will have at least 80% power to detect a difference, if the true response rates are 57% in secukinumab 150 mg group and 40% in placebo. The above sample size calculation is based on Fisher's exact test.

To compensate for drop-outs and protocol violations, 165 patients per group (=495 total) should be recruited into this trial.

SAS® version 9.4 software was used for the calculation of sample size.

5 Appendix

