5.4 Statistical methodology and assumptions

5.4.1 Crude incidence and 100*(1- α) % confidence interval

For n subjects, each at risk to experience a certain event with probability π , the crude incidence is estimated as $p=x/n$, where x is the number of subjects with the event.

Absolute and relative frequencies will be displayed as well as 95% confidence interval for the relative frequency based on the score method including continuity correction (Newcombe 1998).

With z as $(1-\alpha/2)$ -quantile of the standard normal distribution (SAS: $z=PROBIT(1-\alpha/2)$), n as total number of subjects (i.e. number of subjects in the denominator), and p as estimated crude incidence (number of subjects with event / n) it is $q=1-p$.

Then the lower limit is

$$L = \max\left(0, \frac{2np + z^2 - 1 - z\sqrt{z^2 + 2 - \frac{1}{n} + 4p(nq+1)}}{2(n+z^2)}\right)$$

and the upper limit is

$$U = \min\left(1, \frac{2np + z^2 + 1 + z\sqrt{z^2 + 2 - \frac{1}{n} + 4p(nq-1)}}{2(n+z^2)}\right).$$

Note: if $p = 0$ then $L = 0$ and if $p = 1$ then $U = 1$.

If appropriate, an exact $100*(1-\alpha)\%$ confidence interval (Clopper-Pearson 1934) will be obtained by using the SAS procedure PROC FREQ with the EXACT BINOMIAL statement. However, the confidence interval derived via the score method including continuity correction will be the default in safety analyses.

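### Response rates pooled on the logit scale have no rule for cells where only some imputations are 0% or 100%, and no confidence interval where all are

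*SAP*

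**What the plan says.** SAP Section 5.6.1 (Primary analysis, Multiple Imputation) creates 100 completed data sets. For each arm, visit and imputation, PROC FREQ gives a response proportion p and its standard error se. The code takes log(p/(1-p)) and se/(p(1-p)), combines them with Rubin's rules and transforms back.

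A note then covers cells, defined by response variable, arm and visit, in which every response is imputed to 0 or every one to 1. These are to be looked at separately, and the stated result is: "The combined final response rate would be the same as the original response but the 95% CI will be undefined". Nothing is said about a cell where only some of the imputations reach 0% or 100%.

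Three other places bear on this:

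- The same PROC FREQ call asks for a continuity-corrected Wilson interval for each imputation.
- Section 5.4.1, written for crude incidence, gives a continuity-corrected score interval as the safety default and an exact interval where appropriate: "Clopper-Pearson 1934) will be obtained by using the SAS procedure PROC FREQ with the EXACT BINOMIAL statement".
- Shortly after the pooling code, and directly after a sentence on non-responder imputation, Section 5.6.1 adds that "the above analysis will also be performed for each baseline variables (e.g: sex, age class, disease severity at Baseline", which can create small cells.

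**The concern.** The logit and its standard error are undefined at p = 0 or p = 1. This has two consequences.

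First, a cell at 0% or 100% in all imputations would be printed with a rate and no interval. Such a cell looks exact, although in a small category it is very imprecise.

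Second, if only some imputations are at 0% or 100%, those have no value to pass to PROC MIANALYZE. The pooled rate would then rest on the remaining imputations, which are by construction those further from the boundary.

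At stake are the descriptive response tables: early visits for the stricter endpoints (Section 2.7.3 applies multiple imputation to ASAS 40, BASDAI 50 and ACR 20 up to Week 12, and Section 2.7.2 asks for summaries by visit) and small baseline categories from Section 2.3.2, such as age 75 and older or BASDAI above 8.5, each split over three arms.

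**Working it through.** **Plan's own figures.** Section 3 states 92% power with 150 per group for 60% versus 40%, and "the second test will have at least 80% power to detect a difference" for 57% versus 40%. Enumerating Fisher's exact test, two-sided 5%, gives 92.9% and 82.6%. Both figures reproduce. They are not in dispute and serve here only to fix the planned Week 12 rates.

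**Step 1: are the full arms at Week 12 exposed?** With 165 per arm (Section 3), the chance of no responders at a 40% rate is 0.6^165 = 2.5e-37. The chance of all responders at 60% is the same. No imputation will be degenerate.

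**Step 2: does the transformation fail at the boundary?** At p = 0 the code needs log(0), and se = 0 gives 0/0. At p = 1 the logit denominator is zero, and the standard error is again 0/0. In addition, PROC FREQ is asked for level 2 of the response, and a cell with a single response value has no second level. By either route there is no usable estimate. This is read from the code; it was not run in SAS.

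**Step 3: all imputations at 0% or all at 100%.** Between-imputation variance is zero, so a single-sample interval applies. For 0/n the Clopper-Pearson upper limit is 1 - 0.025^(1/n), and the Section 5.4.1 score formula also gives a value:

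| n | Clopper-Pearson upper | 5.4.1 score upper |
|---|---|---|
| 165 | 2.2% | 2.8% |
| 50 | 7.1% | 8.9% |
| 20 | 16.8% | 20.0% |
| 10 | 30.8% | 34.5% |

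**Step 4: only some imputations at 0% or 100%.** All inputs here are assumptions, because the SAP gives neither cell sizes nor early-visit rates.

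*Simple case.* n = 5, four observed non-responders, one missing patient imputed as a responder in 40 of 100 imputations.

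- Mean over all imputations: (40 × 1/5 + 60 × 0)/100 = 8%.
- Logit pooling over the 40 usable imputations: each has p = 0.20, so the back-transformed result is 20%.

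*Further cases.* Here k missing patients are imputed as responders independently with probability q. The mean rate is (observed responders + kq)/n. The pooled rate is the back-transformed mean logit over the non-degenerate imputations.

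| n | Observed responders | Missing k | q | Imputations lost | Mean rate | Logit-pooled rate |
|---|---|---|---|---|---|---|
| 165 | 0 | 15 | 1% | 86% | 0.09% | 0.64% |
| 50 | 0 | 5 | 5% | 77% | 0.5% | 2.2% |
| 20 | 0 | 2 | 5% | 90% | 0.5% | 5.1% |
| 10 | 0 | 2 | 30% | 49% | 6.0% | 11.4% |
| 10 | 8 of 8 | 2 | 70% | 49% | 94.0% | 88.6% |

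Written out for n = 10, q = 30%: one imputed responder has probability 0.42 (logit of 0.1 = -2.197) and two have 0.09 (logit of 0.2 = -1.386). The mean logit is (0.42 × -2.197 + 0.09 × -1.386)/0.51 = -2.054, which is 11.4%.

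**Step 5: a check on the full arm.** With n = 165, 60 observed responders, 15 missing and q = 40%, the mean rate is 40.0% and the logit-pooled rate is 40.0%. Away from the boundary the two methods agree.

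**The case against.** The best defence is that the SAP saw the problem. Its note sets cells that are all 0 or all 1 apart and keeps the right rate for them. A reader might infer that the note's statement about the combined rate is false, because partly degenerate cells are biased. The text does not support that: the note speaks only of cells where all responses are imputed alike, and there it is correct. A reader might also infer that the SAP says degenerate imputations are discarded. It does not; this follows from the code, and only for the mixed case.

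It is also fair that *undefined* describes the logit interval accurately, and that Section 5.4.1 was not written for imputed efficacy rates. What remains is that the PROC FREQ call in the same step already requests an interval that exists at the boundary, so one could have been named.

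The exposure is uncertain. Section 2.2.1 plans no subgroup of interest, and the final analysis uses only two age classes. The sentence on baseline variables follows the one on non-responder imputation; if it refers to that analysis, there is a single completed data set and no mixed case in those categories. The interval gap in all-0 or all-1 cells would still apply, as would the by-visit tables.

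Finally, the chance that a complete cell is all 0 (for example 36% for n = 20 at an assumed 5% rate, 0.95^20) is not the chance of the biased mixed case. That also requires missing patients, no contrary observed response and disagreement between imputations. The SAP gives no basis for estimating it.

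**Conclusion.** The point holds as a minor one. Section 5.6.1 accepts a missing interval where one exists, and it has no rule for cells where some but not all imputations are at 0% or 100%. In such cells the code, read as written, would push the rate away from the boundary: 20% instead of 8% in the simple example, and between about 0.6 and 12 percentage points over all the assumed cells shown. These sizes depend on assumed cell sizes, missing counts and imputed rates, and on the inference that SAS returns no usable estimate at the boundary.

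It would be wrong to infer that the trial's conclusion is at risk. The Week 12 ASAS 20 odds ratio comes from a separate GENMOD model fitted to each imputation, and Section 5.6.1 names exact logistic regression where separation is a concern. The confirmatory test, type I error and power are untouched.

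**What to change.** In Section 5.6.1:

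1. Take the pooled response rate in **every** cell as the mean of the 100 raw proportions. Using it everywhere keeps the estimator from depending on whether a cell happens to be degenerate.
2. Give a Wilson-type interval based on Rubin's total variance, with the formula written out. One possible form: W = mean of p(1-p)/n over imputations, B = between-imputation variance, T = W + 1.01B, and the Wilson formula with n replaced by P(1-P)/T, where P is the mean rate. In the cell of 5: W = 0.0128, B = 0.0097, T = 0.0226, effective n = 0.08 × 0.92/0.0226 = 3.26, and the 95% interval (normal quantile 1.96) is 0.5% to 61%. It is wide, as it should be.
3. Where all imputations agree at 0% or 100%, report the Clopper-Pearson interval, and state that Section 5.4.1 is extended to efficacy rates for this purpose.
4. Delete the statement that the interval will be undefined.

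Clopper-Pearson is the safer choice in item 3 because the score lower limit printed in Section 5.4.1 is not the mirror of its upper limit: at 165/165 it gives 96.7%, while one minus the upper limit for 0/165 gives 97.2%. That formula should be checked before it is used.

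The cost is a few lines of SAP text and code. There is one small downside: in an all-0 or all-1 cell the interval counts imputed patients as observed, which a table footnote should say.
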